- 8. Blood (separation of serum and blood clot; buffy coat; plasma and red blood cells) and urine to be processed within 8 hours at the University of Maryland, Department of Pathology. Four 2 cc aliquots of heparinized blood will be preserved. The red-green top tube will be sent to LHC within 24 hours for lymphocyte culture
- 9. If subject is re-contacted at a later time for additional phlebotomy, then an additional \$25 incentive is given. If subject is contacted for additional questionnaire information, then no incentive is given

RE-CONTACTING SUBJECTS FOR ADDITIONAL INFORMATION OR BLOOD

NCI IRB Approval:	October 28, 2004
Protocol Number:	05-C-N021

[figure not shown]
The interviewer who administered the questionnaire will be the person who will recontact the subject. This re-contact will not involve a script because of the large number of possible circumstances. Subjects will be re-contacted only under certain conditions. The conditions are as follows:

- 1. If there is missing information in the questionnaire
- 2. If the provided information is illegible
- 3. If there is a discrepancy between questionnaire and medical record information
- 4. If there is an obvious inconsistency in the answers to two similar questions in the questionnaire
- 5. If an insufficient volume of blood has been collected
- 6. If there has been mishandling of a blood sample in the laboratory
- 7. If there has been an accident leading to the loss of a blood sample
- 8. If the analysis of a blood sample returns a highly unusual result

We will not contact subjects, who refused to answer questions during the interview process, for responses to those questions they refused. Missing information due to refusal will be marked as such in the questionnaire. We will also not contact a person who failed to complete the sexual history part of the questionnaire.

PROCEDURES

- 1. Subject is contacted by phone, or by letter, notifying him of the need for additional information or blood. If notified by letter, we will include a postage paid envelope and form to be returned if the subject does not want to be contacted
- 2. If only additional information is requested, we will ask the subject by phone for the information. This will be done at the first phone contact, or two weeks after the notification letter was sent out
- 3. If subject agrees, then additional phlebotomy can be done at the home or in the hospital, whichever is convenient

[figure not shown]
[figure not shown]

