3.1 STUDY DESIGN

We are proposing an epidemiological case-control study in which we collect 1) questionnaire information and 2) blood and urine samples from all subjects, and 3) tumor specimens from cases if available. Additional information for cases will be abstracted from medical and pathology records. The duration of the recruitment phase is 5 years. Research laboratory studies will begin at the end of the recruitment phase. The design of the study is illustrated in Figure 3.

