The University of Maryland contractor will train the interviewers for the event that a subject will become emotionally upset during the interview. Part of this training will focus on the scientific background of the study, i.e., the rationale asking these specific questions. We have found that well-informed interviewers are often able to reassure subjects that the information being sought in the interview is needed for the scientific hypotheses that are under study. The interviewer will then be well prepared to answer questions that relate to the sexual history part on pages 18-20 of the supplemental questionnaire. If a subject continues to show signs of distress during the interview, the interviewer will explain that the subject has the right not to answer a question or section of the questionnaire if the subject does not feel comfortably to do so. Indeed, the questionnaire has a special code to denote that the respondent declined a particular question. The interviewers are trained to handle this with neutrality. If the interview is conducted on the premises of the University of Maryland and the Veteran Affairs Hospital, the interviewer will be able to call for help in the event that the above steps have failed to deal with a distressed subject. We have established a list of contacts. [name], [name], and [name], can be called for immediate help. [name] will accept quick referrals and, if requested, will follow up on the incident in a special appointment with the subject. [name] are psychologists at the University of Maryland School of Medicine. [name] is a counselor for patients who have a sexual dysfunction. [name] is a counselor for cancer patients. In the event that an interview takes place off site, e.g., at a subject's home, and the subject has become distressed, the same contact people will be available by telephone.

The list of contacts is as follows:

- 1) [name] (Psychologist), [contact] or [contact] (pager)
- 2) [name] (Psychologist), [contact]
- 3) [name] (Field Supervisor), [contact]
- 4) [name]. (Project Director), [contact]

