5.1.2 QUESTIONNAIRE DATA

The questionnaire data are entered into the survey database twice with a different data entry person each time. If a discrepancy occurs, a supervisor will verify the correct entry. Prior to entry, all questionnaires are coded and edited using a standardized code for occupation, illness, and medication. When appropriate, we utilize the ICD-9 codes (or further updated codes as they become available in the future). A coder will highlight all sections in a questionnaire that contain either an illogical response or missing data. The highlighted sections will be reviewed by a supervisor, or the Research Study Coordinator where needed. A patient may be re-contacted to clarify an answer or to complete a missing response. The supervisor will also examine the coding of about ten percent of the questionnaires. The questionnaires are then entered into the database and verified by the Epi Info software. A contractor to the University of Maryland developed the Epi Info software is programmed to include range checks, skip patterns, and codes for missing data and don't know answers. If errors are detected, a supervisor will assist with the correction. Monthly reports on coding and editing, data entry and the verification status are prepared and presented at monthly staff meetings and site visits.

NCI IRB Approval:	October 28, 2004
Protocol Number:	05-C-N021

During the study, quality control will consist of data comparisons among interviewers to determine the quantity and quality of information that they have gathered, by evaluating characteristics such as interview duration, number of interview problems reported, number of refusals, distribution of subject answers, and number of missing and incomplete answers. In addition, a small random sample of subjects will be re-contacted to inquire about the interview experience, to note any problems, and to confirm that the interview actually took place. Quality assessment will follow procedures that are already in place for the lung cancer study.

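### Questionnaire answers are re-asked without a script by an interviewer who knows case status, one trigger as written reaches only cases, and no flag for recovered answers is described

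*Protocol*

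**What the plan says.** The rules for re-contact are in Protocol section 2, under the heading on re-contacting subjects for additional information or blood. On who calls: "The interviewer who administered the questionnaire will be the person who will recontact the subject". On how: "This re-contact will not involve a script because of the large number of possible circumstances". Where only information is needed, it is requested by phone.

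Eight conditions permit a re-contact. Conditions 1 to 4 concern questionnaire content:

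- Condition 1: "If there is missing information in the questionnaire".
- Condition 2: an illegible entry.
- Condition 3: "If there is a discrepancy between questionnaire and medical record information".
- Condition 4: "If there is an obvious inconsistency in the answers to two similar questions in the questionnaire".

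Conditions 5 to 8 concern blood samples. Items the man refused, and an unfinished sexual history section, are not pursued.

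Section 5.1.2 repeats the permission: "A patient may be re-contacted to clarify an answer or to complete a missing response". On interviewer training, section 3.1.1 states: "Part of this training will focus on the scientific background of the study, i.e., the rationale asking these specific questions". On medical records, section 3.1 states: "Additional information for cases will be abstracted from medical and pathology records".

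**The concern.** At the first interview the questions are printed, trained interviewers administer them, and the man has a copy to follow. At re-contact that common wording is given up by rule, for exactly the answers that were absent or doubtful. The caller knows whether the man has prostate cancer and why each question is asked. If doubtful answers are probed differently in cases and controls, the result is differential misclassification, which can move an exposure odds ratio in either direction.

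The protocol's overview puts environmental exposures, infections, medical history and their interactions with genes into the primary hypothesis. The questionnaire supplies much of that information, as well as covariates for the adjusted models in section 5.4.3.

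**Working it through.** The protocol gives no figure on this point, so there is none to reproduce. The check has two parts: what the text fixes, and how large an effect could be under stated assumptions.

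**What the text fixes**

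1. *Knowledge of case status.* The case procedures in section 2 have the interviewer screen the medical record and record tumor histology. The opening of section 2 has an interviewer determine control eligibility. (That opening gives case eligibility to a nurse, but the case procedures still have the interviewer contact the case and conduct the interview.) No blinding is described.
2. *Knowledge of the rationale.* Section 3.1.1 trains interviewers in it and expects them to be able to refer to the hypotheses when reassuring a subject.
3. *Does the reason for having no script fit?* It fits conditions 5 to 8, where circumstances do vary. It fits conditions 1 to 4 less well, because the item at issue is a specific printed question. For condition 1, re-reading is enough. For conditions 3 and 4, re-reading one item may only reproduce the conflict, so a clarifying step is needed, but that step can be fixed in advance.
4. *Is the trigger symmetric?* Condition 3 needs record information. Abstraction is described for cases in section 3.1 and in the case procedures of section 2. The control procedures describe none, although controls also sign a health-information authorization. As written, cases can be questioned again for a reason with no described counterpart in controls.
5. *Is there a trace?* Section 5.1.2 has a coder highlight illogical or missing answers before data entry and a supervisor review them. Retention of both answers, or a flag on the recovered one, is not described.
6. *Would quality control show it?* Section 5.1.2 compares interviewers with one another and re-contacts a small random sample about the interview experience. No comparison by case status is named.

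**Possible size (assumed inputs)**

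The protocol gives neither a re-contact rate nor a shift. Let f be the share of cases re-asked on an item and d the rise in the proportion answering yes among those re-asked, with no shift in controls. True odds ratio 1, prevalence 0.20 (assumed), 1000 per group (section 5.4.1), two-sided alpha 0.05.

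- Case prevalence: p = 0.20 + f × d
- Odds ratio: OR = [p/(1 − p)] / [0.20/0.80]
- z = (p − 0.20) / √{[p(1 − p) + 0.20 × 0.80]/1000}
- False-positive rate = Φ(z − 1.96) + Φ(−z − 1.96)

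Worked case, f = 0.10 and d = 0.10: p = 0.21. OR = (0.21/0.79)/0.25 = 1.06. z = 0.01/√[(0.1659 + 0.16)/1000] = 0.01/0.01805 = 0.554. Rate = Φ(−1.406) + Φ(−2.514) = 0.080 + 0.006 = 8.6%.

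| Re-asked (f) | Shift (d) | p | OR | False-positive rate |
|---|---|---|---|---|
| 5% | 10 points | 0.205 | 1.03 | 5.9% |
| 10% | 10 points | 0.210 | 1.06 | 8.6% |
| 20% | 20 points | 0.240 | 1.26 | 58% |

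A second model uses the 25% exposure prevalence of section 5.4.2 and lets a share s of re-asked unexposed cases be recorded as exposed, so p = 0.25 + f × s × 0.75:

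- f = 2%, s = 10%: p = 0.2515, OR 1.01, rate 5.1%.
- f = 10%, s = 20%: p = 0.265, OR 1.08, rate about 12%.
- f = 20%, s = 30%: p = 0.295, OR 1.26, rate about 62%.

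Both models agree: negligible when re-contact is rare, material only when it is common and strongly differential.

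**The case against.** The strongest reply is that the harm is inferred. Having no script does not mean that printed items will be reworded or that cases will be probed harder. The interviewers have a procedure manual, which is not available here and could contain re-ask wording. A coder and a supervisor, not the interviewer, identify the doubtful answers. Refused items and the sexual history section are protected. Interviewers are equally unblinded at the first interview, so re-contact adds only the free wording and the case-only trigger.

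Most of this stands as a limit on size. It does not remove the point, because the protocol states a positive rule against a script, and none of these safeguards standardizes what is said on the call or makes condition 3 symmetric.

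A reader might also infer more than the documents support:

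- *That recovered answers can never be identified.* The protocol is silent on a flag, and section 5.1.1 keeps the forms on file. The supportable statement is that no flag is described.
- *That false positives will be frequent.* The 58% and 62% figures need 20% of cases re-asked on the same item and a large case-only shift, and nothing in the protocol supports either.
- *That genotype results are in doubt.* Main-effect genotypes and laboratory measures do not come from the questionnaire.
- *That the protocol defeats a safeguard it names.* It never says that the questionnaire is there to prevent interviewer bias; that is a fair inference from its standard administration.

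Finally, every illustrated odds ratio is below the 1.5 that section 5.4.2 sets as the design target. That limits the consequence, but a biased odds ratio below 1.5 can still pass a 0.05 test.

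**Conclusion.** The concern holds in a limited form. Unscripted re-asking by an informed, unblinded interviewer, with one trigger that in practice reaches only cases and no described flag, leaves questionnaire exposures, their interactions with genotype and adjustment covariates open to differential misclassification that could be avoided at little cost.

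The size is unknown. The central illustration is an odds ratio of about 1.06 and a false-positive rate of about 9% for a null exposure. It rests on an assumed 20% prevalence, 10% re-asked, a 10-point shift and no shift in controls. The firmest element, condition 3, needs no assumed figure: it follows from where the protocol describes record abstraction. This is a worthwhile improvement, not a threat to the main genetic comparison.

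**What to change.** 1. Limit the no-script rule to scheduling and to blood requests (conditions 5 to 8).
2. For conditions 1 to 4, have the interviewer read the printed question and response options again, and both questions when two answers conflict. One fixed neutral clarifying probe follows, the same for cases and controls, which does not disclose what the medical record says.
3. Keep the original and the re-contact answers, flagged with the condition that triggered the call. The flag should be set when the answer is collected.
4. Report re-contact rates by case status.
5. Repeat the main exposure odds ratios using the original answers for items re-asked under condition 3 and, as a sensitivity check, without any recovered answers.

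The cost is a short change to the protocol and interviewer manual, a flag field in the survey database with both answers stored, and slightly longer calls. The run without recovered answers adds some missing data, which may itself be selective, so it should support the main analysis and not replace it.

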We are conducting an epidemiological prostate cancer case-control study in Baltimore, Maryland. Participants will be African-American and Caucasian males who reside in Baltimore city and surrounding areas. The study is ongoing and will recruit 1000 prostate cancer cases and 1000 population-based controls. The cases are recruited at two Baltimore hospitals, the Veterans Affairs Medical Center and the University of Maryland Medical Center. Cases will have pathologically confirmed prostate cancer. The population-based controls are identified through the Maryland Department of Motor Vehicle database, and are frequency-matched by age and race to cases. Enrollment of controls started concurrently with case accrual. The first 12 months of the study constituted a pilot study, during which we evaluated the recruitment procedures. The study involves the administration of a survey and collection of blood from all study subjects. The survey evaluates family cancer history, tobacco use, medication, occupational history, socioeconomic status, and risk factors for prostate cancer. Freshfrozen tumor specimens will be obtained from cancer patients if available. The study is supported by an epidemiological infrastructure that has been developed by our resource contractor at the University of Maryland for a lung cancer case-control study. This lung cancer study is ongoing, and the controls that are recruited for the prostate cancer study are joint controls with the lung cancer study. Hence, population-based male controls recruited by our contractor have double eligibility for the concurrent lung and prostate cancer studies. To achieve an age and race matching of cases and controls in the prostate study, we will over-sample male controls in the lung study.

We will test the primary hypothesis that genes and environmental exposures, including infections and medical history, and interactions between these factors modify prostate cancer susceptibility and contribute to the excessive disease risk among African-American men. As the secondary goal, we will study gene expression profiles of prostate tumors to identify changes in tumor biology that are associated with exposure to genetic and environmental risk factors. It is a focus of this research to identify mechanisms in tumor biology that may cause the aggressive nature of prostate cancer in African-American men.

TABLE OF CONTENTS

1 1.1 1.2	INTRODUCTION STUDY OBJECTIVES BACKGROUND AND RATIONALE	5 7 8

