After the eligibility has been confirmed, a nurse will contact patients to get both informed consent and authorization to obtain, use and disclose protected health information for research. A trained interviewer and phlebotomist will administer the questionnaire to those who consented. After the interview, blood will be collected. The investigators will make every effort to obtain informed consent and administer the questionnaire well in advance of either a scheduled surgery or an alternative treatment such as radiation or hormone therapy. Most of the patients will not be rushed to surgery. The disease is detected by needle biopsy and patients may seek a second or third opinion before they decide on a treatment option. Thus, we will have the opportunity of recruiting most patients weeks or months before either a surgery is scheduled or an alternative treatment will start. It is always at the discretion of the patient to give informed consent on one day but to have the interview or the blood collection on another day that is convenient for him. In the situation where we cannot get access to an eligible patient well in advance of surgery, we will approach the patient up to one day before surgery to seek consent. We will offer to administer the questionnaire and obtain blood after the surgery. However, if the patient wishes to be interviewed and have the blood drawn at the same day when he gives informed consent, we will do so. If we would limit our access to surgery patients because of a longer waiting period where we do not approach eligible cases prior to surgery, it could seriously compromise our ability of collecting the number of fresh-frozen tumor specimens that are needed for our research study.

October 28, 2004 05-C-N021

PROCEDURES

- 1. Interviewer obtains patient's name, location and physician's name
- 2. Interviewer screens medical record for eligibility. If eligible, record age, race and family history. Record reasons for ineligibility. Also record histology of tumor
- 3. Interviewer obtains a non-objection statement from the treating physician to contact the patient. If physician refuses, interviewer records reason for refusal on eligibility record, in addition to age, race, and family history of PCa
- 4. Interviewer contacts case and obtains informed consent and authorization to obtain, use and disclose protected health information for research

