questionnaire to those who consented. Blood and urine will be collected either at the interview or at a separate appointment.

PROCEDURES

- 1. An introductory letter is sent to a prospective subject to notify him of the study
- 2. The subject is contacted by phone to explain the study and how he was selected, and to request participation. The permission to interview the person is obtained. If person refuses to participate (either right away or repeatedly delaying consent [failure to make commitment for 3 requests]), then record brief information about age, race, and family history of lung and prostate cancer. If subject refuses to give the information and also requests that no such information will be kept on file, we will not record this information and will delete any information that already exists on file. However, we will keep a DMV ID number to avoid re-contacting those subjects that refused to participate in our study
- 3. Obtain informed consent and authorization to obtain, use and disclose protected health information for research. This is done either at the study office, or other locations such as person's home or person's work location. If person refuses (failure to make commitment for 3 requests), then record brief information about age, race, and family history of lung and prostate cancer. If subject refuses to give the information and also requests that no such information will be kept on file, we will not record this information and will delete any information that already exists on file. However, we will keep a DMV ID number to avoid re-contacting those subjects that refused to participate in our study
- 4. Perform interview and complete questionnaire. This is done either at the study office, or other locations such as person's home or person's work location. The interviewer will give a copy of the questionnaire to the subjects before the interview begins. Subjects will have the opportunity to read a question while being interviewed. The last section of the questionnaire which is examining sexual history is self-administered. Provide incentive of \$25
- 5. Collect about 55 cc of blood. One 15 cc red top tube, three 10 cc green top tubes and one 10 cc red-green top tube. Place tubes in a thermos for short-term storage and transport
- 6. Collect urine (50 ml)
- 7. Provide incentive of \$25

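### Re-contact on a questionnaire–record discrepancy can, as written, operate only for cases, so self-reported exposures may be measured differently in cases and controls

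*Protocol*

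**What the plan says.** Under the re-contact heading in Section 2, the third of eight conditions is "If there is a discrepancy between questionnaire and medical record information". The same text adds that "The interviewer who administered the questionnaire will be the person who will recontact the subject" and that "This re-contact will not involve a script because of the large number of possible circumstances". Section 5.1.2 gives the purpose of a questionnaire call: "A patient may be re-contacted to clarify an answer or to complete a missing response".

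Records enter the study on the case side. The case procedures in Section 2 state: "Interviewer screens medical record for eligibility. If eligible, record age, race and family history". Section 3.1 states: "Additional information for cases will be abstracted from medical and pathology records". The control procedures go from the motor-vehicle list to letter, telephone call, consent, interview and specimens. Controls sign the same kind of form as cases ("Obtain informed consent and authorization to obtain, use and disclose protected health information for research"), but no later control step obtains or reads a record.

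The opening summary makes these exposures part of the primary hypothesis: "genes and environmental exposures, including infections and medical history, and interactions between these factors modify prostate cancer susceptibility". Section 3.1.1 shows that medical history, medications and family history are collected by questionnaire.

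**The concern.** A case-control comparison of a self-reported exposure needs the answer to be obtained in the same way in both groups. Missing, illegible or internally inconsistent answers (conditions 1, 2 and 4) can arise for any subject. A conflict with a medical record can arise only where the study holds a record. The call is unscripted and is made by the interviewer who did the interview; nothing in the protocol masks that person to case status.

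If such calls change answers, reporting errors are reduced in cases and left alone in controls. That is exposure misclassification that differs by case status, and it can move an odds ratio away from 1 when there is no association. The analyses at stake are the case-control odds ratios for family history, medical history and medications. The protocol does not confine the condition to non-exposure items, does not say which answer is kept for analysis, and does not mention the asymmetry among the limitations in Section 3.1.5.

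**Working it through.** The protocol gives no figure for reporting accuracy, number of discrepancies or share resolved, so there is nothing of its own to reproduce. The check has two parts.

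**1. Where a record is available**

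| Step | Cases | Controls |
|---|---|---|
| Record screened before enrolment | Yes, family history noted (Section 2) | No step |
| Record abstracted afterwards | Yes (Section 3.1; Section 2, pathology review) | No step |
| Authorization signed | Yes | Yes, but no use of it is described |
| Conditions 1, 2 and 4 can arise | Yes | Yes |
| Condition 3 can arise | Yes | Not under any described procedure |

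Family history is the clearest item, because it is the one exposure that the protocol says is taken from the case's record.

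**2. What one-sided correction could do**

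Inputs from the protocol: 1000 cases and 1000 controls (opening summary); two-sided alpha 0.05 and exposure prevalence p = 0.25 (Section 5.4.2). Assumptions: true odds ratio 1; sensitivity Se and specificity Sp of the interview answer, equal in both groups before any call; f, the fraction of erroneous case answers that is corrected.

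- Controls: q0 = p·Se + (1 − p)(1 − Sp)
- Cases: q1 = p[Se + f(1 − Se)] + (1 − p)(1 − Sp)(1 − f)
- Expected odds ratio = [q1/(1 − q1)] / [q0/(1 − q0)]
- Rejection rate: two-proportion z test, pooled variance under the null, both tails, 1000 per group

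Worked example, Se 0.80, Sp 1, f 0.5: q0 = 0.25 × 0.80 = 0.200; q1 = 0.25 × (0.80 + 0.5 × 0.20) = 0.225; odds ratio = (0.225/0.775)/(0.200/0.800) = 0.2903/0.2500 = 1.16.

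| Se | Sp | f | q0 | q1 | Odds ratio | Rejection rate |
|---|---|---|---|---|---|---|
| 0.80 | 1.00 | 0.25 | 0.2000 | 0.2125 | 1.08 | 0.106 |
| 0.80 | 1.00 | 0.50 | 0.2000 | 0.2250 | 1.16 | 0.277 |
| 0.80 | 1.00 | 1.00 | 0.2000 | 0.2500 | 1.33 | 0.764 |
| 0.70 | 1.00 | 1.00 | 0.1750 | 0.2500 | 1.57 | 0.984 |
| 0.90 | 1.00 | 1.00 | 0.2250 | 0.2500 | 1.15 | 0.259 |
| 0.70 | 0.90 | 1.00 | 0.2500 | 0.2500 | 1.00 | 0.050 |
| 0.80 | 0.90 | 1.00 | 0.2750 | 0.2500 | 0.88 | 0.246 |
| 0.90 | 0.90 | 1.00 | 0.3000 | 0.2500 | 0.78 | 0.707 |
| 0.95 | 0.90 | 1.00 | 0.3125 | 0.2500 | 0.73 | 0.875 |

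Correcting omissions pushes the odds ratio above 1, correcting over-reports pushes it below 1, and the two can cancel. With f = 0 in both groups, or the same f in both, q1 = q0: the odds ratio is 1.00 and the rejection rate 0.05.

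**The case against.** A reader might infer that the protocol has case answers overwritten from the record while control answers stand, and that this produces false odds ratios above 1 for medical history. The text does not go that far, for four reasons.

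- The protocol provides for a call to clarify an answer. It does not say that the record prevails, that the answer is replaced, or that the first answer is discarded. Which value is analysed may be settled in a procedure manual or an analysis plan. This stands, and the point is therefore conditional on a change being made. It is still a natural reading, because a call about a discrepancy that could change nothing would serve little purpose.
- Systematic comparison of exposure history with records is not described. The stated uses of records are eligibility with family history, pathology, and stage and outcome. The questionnaire checks in Section 5.1.2 look for illogical or missing responses. This stands: medical history and medications are only possibly affected.
- Control records are not expressly ruled out. Controls sign an authorization, and Section 5.1.1 lists medical reports among the study forms without limiting them to cases. Even so, no control step obtains a record.
- A direction above 1 requires near-perfect specificity, and the larger values also require most case errors to be found and corrected. This stands.

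The reach is limited too. The objective in Section 1.1 concerns genotypes measured from blood, which no telephone call can alter. If exposure is independent of genotype and correction does not depend on genotype, a null multiplicative gene-environment interaction also stays null.

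**Conclusion.** The asymmetry is in the text and no safeguard accompanies it. If condition 3 calls change answers, odds ratios for family history, and possibly for medical history and medications, can be biased by case status. Neither direction nor size can be fixed from the protocol. At 25% prevalence, the settings above span expected null odds ratios from 0.73 to 1.57. Partial correction of omissions at sensitivity 0.80 gives 1.08 to 1.16. Only the setting with poor recall and complete correction (1.57) exceeds the odds ratio of 1.5 that Section 5.4.2 names as the design target. All of these rest on assumed error rates and an assumed share corrected.

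Genotype main effects are not affected. This is a modest flaw in a data-collection rule, worth removing because removal is nearly free. It is not a threat to the genotype analysis.

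**What to change.** Choose one of two changes to the re-contact text in Section 2, and repeat it in Section 5.1.2.

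1. Limit condition 3 to clinical and pathology items, so that it cannot touch questionnaire exposures.
2. Keep condition 3, but state that the answer given at interview is the value for every case-control comparison. Any value prompted by a record goes into a separate field used only in case-only analyses.

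The cost is a sentence or two of protocol wording and, for the second option, one extra database field. The downside is that some case answers known to be wrong stay in the case-control analysis, as undetected errors do for controls. That preserves comparability at some loss of accuracy. A fixed script for every clarification call is not needed for this purpose, and the protocol gives a reason for not having one.
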